#### **4. End-of-study visit**

Each subject will have an end-of-study visit. This does not represent an independent visit, but a simple recording of the end of monitoring for the individual subject, and will coincide with:

- a. the last contact, usually at the center, at the end of the 2-year observation;
- b. the planned or unplanned follow-up visit at which any of the events terminating the follow-up have occurred, as indicated in the unplanned follow-up visit (thrombotic complication, major bleeding complication, substantial change in therapy, other event preventing continuation of the follow-up);
- c. the investigator is informed that the subject died;
- d. the subject ceased reporting to the center and started reporting to another hospital;
- e. the subject moved the residence to a place preventing continuation of the follow-up;
- f. the subject was lost to follow-up without additional information.

##### *8.3.2 Variables*

The variables to be collected in this study are the usual descriptive, diagnostic and prognostic variables normally recorded in the subject's cards, as well as the description of the antithrombotic treatments applied and the reason for change. In the follow-up, the usual outcome variables relevant to the subject's status will also be collected.

###### **a. descriptive variables**

These include age, sex, ethnicity.

###### **b. diagnostic variables**

These include complete description of the index event, including the putative cause of a secondary event and risk factors for the event.

###### **c. prognostic variables**

These include body weight, height and creatinine (to estimate BMI and creatinine clearance); clinical conditions of veins with calculation of the Villalta score; active concurrent diseases, vascular risk factors, medications in long-term use.

###### **d. treatment information**

This includes type, dosage and duration of the maintenance anticoagulation performed; type, dosage and planned duration of the new treatment proposed, if any, and the classification of the reasons considered by the investigator for the decision taken.

###### **e. outcome variables during the follow-up**

These include type and time of contact, classification of the events (thrombotic complications, bleeding complications, survival, hospitalization) occurred in the period since the last contact, and information on the current therapy, if any, and relevant changes regardless of whether decided by the investigator, another physician, or spontaneously by the subject.

##### *8.3.3 Source of data*

The source of data is the information collected into, or to be recorded into, the subject's hospital card or equivalent documents. No additional data are requested.

## 8.4 Data management

The investigators will directly manage the primary data, as usual. The responsibility to properly collect and record the data into the hospital, center or other subject's documents remains with the individual attending physicians. The responsibility to collect, verify and record possible adverse drug reactions remains with the local responsible for pharmacovigilance.

The investigator and/or specifically appointed co-investigator(s) will transfer the study data to the study database. The study data will be entered into an e-CRF, accessible from a standard personal computer with the use of standard browsers. The database will be unique and centralized, to facilitate maintaining proper database security with the usual maintenance procedures (data encryption, backups, checks of consistency and integrity, etc.). All data to be transferred will be anonymized; only the investigator and co-investigators will locally retain a log in which the correspondence between the study unique code and the subject's identification will be possible. This log will not exit the hospital, but shall be kept available for possible verifications within the frame of the quality assurance procedures (§ 8.5).

Each investigator and duly delegated co-investigator will have a personal username and password allowing access to the centralized database. All investigators at one Center can have access to the data of their center. In this context, "center" means an operating unit in which one or more investigators monitor a number of subjects, who are not seen for the same reason by other units.

## 8.5 Quality assurance

This is an investigators-initiated study; therefore, each investigator assumes the responsibility to guarantee the quality of the data recorded in the subject's documents. The National coordinator, in accordance with the local investigator, may require to inspect and verify the core data, in particular the subjects' log and the informed consent forms. The local database operators assume the responsibility to guarantee the quality of the data conferred to the central database in accordance with the procedures setup in the database manual. The statistical responsible of the study will verify completeness, accuracy and plausibility of the data recorded onto the database, producing if needed requests for additional verification against the raw data recorded in the subjects' documents. Only after the final verification after the study closure, the database will be frozen and submitted to statistical analysis.

# 9. Protection of the subject's rights

The study will be performed in compliance with the Declaration of Helsinki (<http://www.wma.net/en/30publications/10policies/b3/>) and the applicable sections of the Good Clinical Practice, as well as in compliance with the international and national regulations.

## 9.1 Study conduct

This is an observational study in which the medications prescribed, if any, are prescribed by the attending physician according to the relevant Authorization to Commercialization, in the best subject's interest, based on the training and expertise of each physician. No diagnostic or therapeutic action is anticipated by this protocol, which are not normally planned for the appropriate monitoring and follow-up of the subjects.

## 9.2 Ethics Committee/Institutional Review Board

Each center participating in this study should obtain the authorization to participate by the relevant EC/IRB. Copy of this authorization shall be sent to the promoter of the study and also kept by the investigator until the end of the study, and may be subject to verification by the National Coordinator. In case of protocol amendments, it is the Investigator's responsibility to submit such amendments to the relevant EC/IRB, according to the Center's procedures.

### 9.3 Informed consent

Before conferring any data to the study database, the investigator shall obtain the consent from each subject, after having supplied adequate information. To be recruited, the subjects must have given the individual consent in writing to the management of personal data in anonymous and aggregate form. Each subject shall be informed that can withdraw the consent at any time of the study, without penalties and without justification (§ 8.2.4). The information sheet and the consent form to the use of personal data are appended to this protocol. The documentation of consent shall be archived by the local investigator until the end of the study, and may be subject to verification by the National coordinator. It is responsibility of the Investigator's or a delegate to record onto the database that the consent was obtained, with the relevant date, and to inform the study promoter of the recruitment of a new subject according to the protocol. This information, however, is associated in the database to the subject's unique study code, without personal identification data.

### 9.4 Subjects insurance

This study collects data on the routine management of subjects with drugs used in the indications authorized, at doses and in dosage forms duly authorized. The diagnostic, therapeutic and monitoring procedures of the study follow the routine planned for these subjects. The participants do not incur into any additional risk or discomfort because of their participation in the study. Consequently, no specific insurance is needed.

### 9.5 Confidentiality

All subjects managing the study data guarantee to maintain the confidentiality of the subjects' personal data. In particular, the investigator and co-investigators, who have access to sensible data, guarantee to keep confidential any information they might become aware of, as in the normal clinical practice. The entire documentation available outside the center is instead anonymized and does not contain information that might allow identifying the participating subjects.

## 10. Statistics

### 10.1 Statistical considerations

The statistical analyses will be descriptive and exploratory. Given the nature of the study, which is observational, it is not designed to confirm or reject predetermined hypotheses. The hypothesis indicated in the sample size calculation is to be considered supportive of the physicians' attitude towards methods of long-term prophylaxis, to be eventually confirmed by specifically designed motivational investigations.

### 10.2 Sample size

The study anticipates recruiting approximately 3,200 subjects, based on considerations relevant to the primary endpoint.

The primary endpoint is the decision taken by the attending physician at the end of the maintenance anticoagulation initiated after the index event. Three options are possible: continue with extended anticoagulation (regardless of individual drug and dose), replace the anticoagulation with an antithrombotic, non-anticoagulant treatment, or stop any pharmacological prophylactic treatment.

In absence of other determinants, the null hypothesis is that the distribution of subjects by option is uniform. The analysis can therefore be performed with a goodness-of-fit test with 2 degrees of freedom. The alternative hypothesis is that at least one of the three choices is selected in a greater proportion than the other two. This analysis is performed once only at the end of recruitment.

With approximately 3,200 subjects, the study has 90% power to detect with 95% confidence a deviation from the uniform distribution, in case one of the options is selected in a proportion exceeding by 10% relative or more the proportion expected from the uniform distribution (i.e., in 36.3% or more of the subjects) [7].

Given that the factor “country” (synonymous of “healthcare system”) will be a likely cofactor in the analyses, the sample should be split across the participating countries in such a way to allow a reliable representativeness also for the smaller countries. The limit was considered not less than 100 subjects per country. The anticipated contribution by country was therefore estimated as:

Country	cases
China	approximately 200
Czechia	approximately 350
Mexico	approximately 300
Poland	approximately 900
Portugal	approximately 350
Romania	approximately 250
Russia	approximately 800
Slovakia	approximately 150
Tunisia	not less than 100

Since in this study the secondary endpoints are of clinical relevance as well, it is appropriate to estimate whether the indicated sample can yield reliable information also in relation to such endpoints.

The secondary endpoints are the rate of thromboembolic complications and the combined rate of bleeding complications/death. To allow the DMSB (§ 11.3) to take appropriate decisions on the conduct of the study, these analyses will be performed at yearly intervals, i.e., when the last recruited subject has reached the end-of-year observation. There will therefore be 2 analyses (1 interim and one final), so that the final analysis will have to report as statistically relevant and deserving further investigations,  $P$ -values  $\leq 0.048$ .[8]

The interest of the study is to find whether any of the three constituted sub-populations – extended anticoagulation; long-term antithrombotic prophylaxis; no pharmacological prophylaxis (§ 8.1) – deviates from the expected risk, to an extent deserving investigation of the potential predictors of outcome.

From the literature [2, 3], the estimated annual risk of recurrence in the control group was approximately 5 events per 100 subject-years. The combined risk of bleeding or death was approximately 1 event per 100 subject-years.

Assuming that almost all recruited subjects will be monitored for at least one year, this survey has 80% power to detect with a two-tailed 95% confidence (after accounting for the interim analyses) a Cohen’s effect of the baseline decision taken on the follow-up outcomes, of 0.055 [9]. It can therefore identify as potentially relevant, deviations of at least one of the constituted sub-population from the anticipated recurrence rate of at least  $\pm 0.0123$  (3.77 or less, or 6.23 or more, events per 100 patients per year). Similarly, it has 80% power to detect with a two-tailed 95% confidence a deviation of at least one of the three constituted sub-populations from the anticipated bleeding/death rate of  $\pm 0.0055$  (0.45 or less, or 1.55 or more, events per 100 patients per year). [10]

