## 6. Rationale and justification

### 6.1 Background

The reference international guidelines [1] recommend initial treatment of DVT of the lower limbs and/or PE with a direct anticoagulant (oral or parenteral) followed by a period of anticoagulation therapy with the same direct oral anticoagulant or partially overlapping it with a Vitamin K antagonist (VKA), with a preference for the former alternative.

An exception is represented by a VTE associated with an active cancer. In this case, a treatment with parenteral anticoagulant (in particular LMWH) for the whole period of 3 months is recommended.

Anticoagulation therapy is essential for at least three months in all cases. The incidence of VTE recurrence is considered to be very low when an event is triggered by surgery or another specific risk factor. In these cases, a three-month treatment is considered sufficient. In case of idiopathic (unprovoked) events, however, such period may not be sufficient due to the marked tendency of VTE to recur. In these cases, it is advisable to assess each subject's specific benefit (expected decrease in recurrences) in comparison with the risk of bleeding associated with prolonged anticoagulation, and determine the duration of anticoagulation based on this evaluation. However, pre-determined time-limited courses of therapy longer than 12 months are unusual [1]. In addition, based on the local healthcare system, not all regimens can be protracted indefinitely in all cases.

At the end of the three months – or longer, usually not more than one year – of anticoagulation, the attending physician has to decide whether and how to manage the long-term secondary prevention of recurrences, based on an assessment of the individual ratio of risks of recurrence and of bleeding. These individual estimates are often difficult to evaluate. A number of additional factors also influence the decision, including subject's predicaments and preferences, concurrent diseases and treatments, healthcare system support, and availability of potentially effective alternative treatments, such as aspirin [2] and sulodexide [3].

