### 8.2.2 Inclusion criteria

Subjects meeting all of the following criteria qualify for entry into the study:

- a) subjects who provided a written informed consent and authorization for disclosure of protected health information;
- b) male and female adult or elderly subjects ( $\geq 18$  years at the time of signing the informed consent; no upper limit);
- c) of any ethnicity;
- d) with a first-ever event of provoked or unprovoked DVT of the lower limbs and/or PE treated with anticoagulants (NOACs, VKAs, or LMWHs) according to the local procedures (usually for 3 to 12 months) and to be re-evaluated to decide the treatment to be prescribed after this period;
- e) for whom the center possesses all the data relevant to the index event;
- f) having a permanent reference contact.

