## 10.3 Populations

As usual in the observational studies, the analyses will be performed on the total sample monitored. Only subjects specifically indicated by the Steering Committee as major, irreconcilable deviation will be excluded from analysis (§ 11.1). Missing data will not be replaced. Subgroup analyses are not anticipated, however – given the exploratory nature of the study – unplanned subgroups analyses may be performed *post-hoc*, upon indications by the Steering Committee.

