### 10.4.3 Secondary endpoints

The secondary endpoint analyzable at the completion of recruitment is the reason(s) justifying the choice analyzed in 10.4.2. These will be tabulated by choice and compared, if appropriate, by chi square test or by ordinal logistic regression. Unplanned *post-hoc* subgroup analyses may be performed if requested by the Steering Committee.

The other secondary endpoints include the frequency of thromboembolic complications and the frequency of bleeding complications or death for any reason. These will be analyzed at the completion of each year of observation (full year of observation of the last subject entered into the long-term follow-up). The interim results will be used by the DMSB to decide on whether the observation has to continue or must be stopped. The final analysis will be adjusted for multiplicity using the nominal critical P value of 0.048.

Event rates will be reported at the available observations as proportion, stratified by sub-population, with the relevant confidence interval. Deviations from the expected rate of events will be analyzed by chi square and/or time to event by survival analysis. If appropriate, subgroups will be analyzed with the Cox survival model. Impact of putative predictors as indicated by the Steering Committee will be analyzed by logistic regression and/or Cox proportional-risk model.

Since clinically-relevant non-major bleeding may not be a reason for interrupting the follow-up, and minor bleedings are not a reason for interruption, it is possible that the number of bleeding events per subject can be submitted to analysis by Poisson regression.

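### A single expected recurrence rate of about 5 per 100 subject-years is used for sub-populations that mix provoked and unprovoked index events, so index-event mix alone may produce or hide a deviation

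*Combined protocol and SAP*

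**What the plan says.** Section 10.2 draws the expected recurrence rate from two cited studies: "From the literature [2, 3], the estimated annual risk of recurrence in the control group was approximately 5 events per 100 subject-years". The stated interest is whether any of the three sub-populations (extended anticoagulation, antithrombotic prophylaxis, no drug prophylaxis) "deviates from the expected risk, to an extent deserving investigation of the potential predictors of outcome". Limits of 3.77 and 6.23 events per 100 per year mark a potentially relevant departure. Section 10.4.3 reports rates by sub-population and adds: "Deviations from the expected rate of events will be analyzed by chi square and/or time to event by survival analysis".

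Eligibility in section 8.2.2 covers subjects "with a first-ever event of provoked or unprovoked DVT of the lower limbs and/or PE". Section 6.1 says of the provoked type: "The incidence of VTE recurrence is considered to be very low when an event is triggered by surgery or another specific risk factor". It regards three months of treatment as enough in those cases, and it describes unprovoked events as markedly prone to recur.

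Baseline Form 2/8 in Appendix IV records whether the index event was idiopathic or secondary. No analysis section names that item. Section 10.3 states "Subgroup analyses are not anticipated", although the same sentence goes on to allow unplanned post-hoc subgroups at the Steering Committee's request. Section 10.4.3 also provides for Cox and logistic models with predictors chosen by that committee.

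**The concern.** If recurrence depends on index-event type, as section 6.1 says, one fixed rate can be the right expectation for only one provoked/unprovoked mix. The plan gives neither the mix behind the 5 per 100 nor the mix expected in any decision group. A departure from 5 may then reflect who is in the group rather than anything about the subjects' risk given their type of event. Equally, a low-risk provoked fraction may dilute a truly raised rate among unprovoked subjects, so that nothing is flagged.

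Section 6.1 also gives a reason to expect provoked cases to gather among those who stop, since a short course is considered sufficient for them. That is a suggestion, not a demonstrated fact. What is at stake is how the recurrence results are read against the expected rate. The group rates themselves are unaffected.

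**Working it through.** **Inputs from the documents**
- Benchmark 5 per 100 subject-years; limits 3.77 and 6.23 (section 10.2).
- Total size: "The study anticipates recruiting approximately 3,200 subjects, based on considerations relevant to the primary endpoint".
- Final critical P value 0.048 (sections 10.2, 10.4.3 and 11.3; the Synopsis gives 0.03, and the body's value is used here).
- Almost all subjects followed for at least one year (section 10.2).

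**Assumptions, because the documents give no figure**
- Equal split: 3,200 / 3 = about 1,067 subjects, one year each, so 1,067 subject-years.
- Provoked rate rP of 1, 2 or 3 per 100; unprovoked rate rU of 5, 6, 7 or 8 per 100; provoked share s of 25% or 50%.
- Recurrence depends on index-event type only, with no effect of the decision.

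**1. The plan's own figure.** Section 10.2 claims 80% power for a Cohen "effect of the baseline decision taken on the follow-up outcomes, of 0.055". The non-centrality is 3,200 × 0.055² = 9.68. With 2 degrees of freedom, power is 80.2% at alpha 0.05 and 79.7% at 0.048, so the claim reproduces. The conversion 0.055 × √(0.05 × 0.95) gives 0.0120, close to the stated 0.0123.

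**2. Share that reaches the lower limit.** The pooled rate is r = (1 − s) × rU + s × rP. Setting r = 3.77 gives s = (rU − 3.77) / (rU − rP). With rU = 5:
- rP = 1: 1.23 / 4 = 31%
- rP = 2: 1.23 / 3 = 41%
- rP = 3: 1.23 / 2 = 62%

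**3. Chance of a flag.** As an illustration, take an exact two-sided Poisson test of 5 per 100 at P ≤ 0.048. Expected events are 1,067 × 0.05 = 53.35. The test rejects at 38 or fewer, or 69 or more, events, with tail probabilities of 1.7% and 2.2% and an actual size of 3.9%.

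| rU | rP | s | Pooled rate | Expected events | Flagged low | Flagged high |
|---|---|---|---|---|---|---|
| 5 | 1 | 25% | 4.00 | 42.7 | 27% | <1% |
| 5 | 2 | 25% | 4.25 | 45.3 | 15% | <1% |
| 5 | 3 | 25% | 4.50 | 48.0 | 8% | <1% |
| 5 | 1 | 50% | 3.00 | 32.0 | 87% | <1% |
| 5 | 2 | 50% | 3.50 | 37.3 | 59% | <1% |
| 5 | 3 | 50% | 4.00 | 42.7 | 27% | <1% |
| 6 | 2 | 25% | 5.00 | 53.35 | 1.7% | 2.2% |
| 8 | 2 | 50% | 5.00 | 53.35 | 1.7% | 2.2% |
| 8 | 2 | 25% | 6.50 | 69.4 | <1% | 53% |

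So mix alone can push the result down, leave it unchanged, or push it up.

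**4. Masking.** Suppose unprovoked subjects recur at 7 per 100. With no provoked cases, 74.7 events are expected and a high flag has a 76% chance. With 25% provoked, the pooled rate is 5.50, 5.75 or 6.00 at rP = 1, 2 or 3, and the chance of a high flag falls to 10%, 18% or 28%.

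**The case against.** Several counter-arguments have force.

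- **The analysis is exploratory.** Section 10.1 says the study is not designed to confirm or reject hypotheses, and section 10.2 treats a deviation as a prompt to look for predictors. The Steering Committee could choose index-event type as a predictor, and post-hoc subgroups are permitted. This stands and lowers the severity. It does not remove the point: index-event type is not named, and nothing prompts a search when mixing has hidden the signal.
- **The mix belongs to the question asked.** Section 7.1 seeks event rates under real conditions among subjects given each option. The overall group rate, mix included, answers that. This stands. Only the comparison with 5 per 100 is affected.
- **The planned test is not clearly one-sample.** Section 10.4.3 gives no number for the expected rate, and the stated power reproduces only with 2 degrees of freedom, which fits a comparison across the three groups. The wording of sections 10.2 and 10.4.3 nevertheless sets each sub-population against an expected rate. The Poisson test above illustrates that reading and is not the protocol's specified method.
- **The low-flag figures assume that the benchmark is an unprovoked rate.** This is correct; the 6/2 and 8/2 rows show other outcomes.

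A reader might infer that provoked cases will concentrate among those who stop, so that stopping will look safer than it is. The documents do not support that. Section 6.2 says little is known about the reasons for the decision, section 7.2.2 says there is no indication of which factors guide it, and section 6.1 calls practice far from standardised. The plan also makes no causal claim about stopping.

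**Conclusion.** The point holds as a conditional one. Comparing every decision group with one rate of about 5 per 100 does not allow for index-event mix, which the protocol itself treats as a major determinant of recurrence. A deviation may appear in either direction, or a raised rate in unprovoked subjects may go unseen, for that reason alone.

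The size cannot be fixed from the documents. Under the assumptions above, the chance of a low flag ranges from 87% (half provoked, rates 5 and 1) to no excess over the test's 3.9% size (half provoked, rates 8 and 2). A high flag reaches 53% with rates 8 and 2 and a quarter provoked. All figures rest on an equal three-way split and one full year per subject; early end of follow-up at a change of therapy would reduce the subject-years.

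The documents do not show which direction will occur, nor that the plan excludes any look at index-event type. Severity is minor to moderate.

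**What to change.** **Section 10.4.3**
- Keep the overall rate by sub-population as the descriptive estimate.
- Add thromboembolic rates per 100 subject-years, with confidence intervals, by sub-population and by idiopathic/secondary index event, using the item on Baseline Form 2/8. Define in the plan what counts as secondary, since the form does not.
- Name index-event type as a pre-specified covariate in the Cox and logistic models.

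**Section 10.2**
- State which index-event population the 5 per 100 describes.
- State that the 3.77 and 6.23 limits apply only to a group with that mix.
- Interpret a deviation from 5 only within the matching stratum. An expected rate standardised to each group's mix is an alternative only if the cited sources give rates by index-event type; the documents do not.

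**Cost.** Wording changes and one extra stratification on a variable already collected, with no new data or subjects. Intervals within strata will be wider, and fewer subject-years will support any comparison with the benchmark than the pooled group suggests.

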Sample size justification	
The primary endpoint is the decision taken by the attending physician at the end of the maintenance anticoagulation initiated after the index event. Three options are possible and in absence of other determinants, the null hypothesis is that the distribution of subjects by option is uniform. The analysis can therefore be performed with a goodness-of-fit test with 2 degrees of freedom. The alternative hypothesis is that at least one of the three choices is selected in a greater proportion than the other two. This analysis is performed once only at the end of recruitment.
 
With approximately 3,200 subjects, the study has 90% power to detect with 95% confidence a deviation from the uniform distribution, in case one of the options is selected in a proportion exceeding by 10% relative or more the proportion expected from the uniform distribution (i.e., in 36.3% or more of the subjects).
 
The study also has 80% power to detect with a two-tailed 97% confidence (accounting for interim analyses) a deviation of at least one of the sub-populations, by at least:
 
 
±1.23 recurrence events from the expected rate of 5 events per 100 subjects per year, and
 
±0.55 bleeding events/deaths from the expected rate of 1 event per 100 subjects per year.
 

Statistical-analytical plan	
Statistical considerations
 
The statistical analyses will be descriptive and exploratory. Given the nature of the

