#### **10.4.4 Other endpoints**

Other monitored endpoints include the occurrence of hospitalization and the change of prophylactic therapy, including:

- institution – by the attending physician or other physician - of a therapy in subjects who stopped any prophylactic treatment at recruitment;
- change – by the attending physician or other physician - of the prophylactic treatment assigned at recruitment, and
- interruption – by the attending physician, other physician or by spontaneous subject's decision - of the prophylactic treatment assigned at recruitment.

Hospitalizations do not necessarily imply interruption of the follow-up, unless associated to a primary endpoint (thromboembolic event, bleeding, death) or result in the impossibility to continue an appropriate monitoring (e.g. need for anticoagulation). Consequently, hospitalizations can be analyzed by chi square across sub-populations as proportion of subjects with event or, in case of an appreciable number of events, by Poisson regression.

Any change in therapy, instead, implies interruption of the follow-up. Changes in therapy will be tabulated, stratified by sub-population, as absolute number and proportion and, if appropriate, analyzed by chi square and/or by logistic regression.

In addition, the reasons for study termination may be considered an endpoint. These will be tabulated by sub-population and compared, if appropriate, by chi square or ordinal logistic regression. If required by the Steering Committee, unplanned *post-hoc* subgroup analyses may also be performed.

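### The 80% power for a deviation of ±1.23 (recurrence) or ±0.55 (bleeding/death) per 100 per year in one sub-population is computed as if that group held all 3,200 subjects; in one third of them, over one year, power is about 39–48%

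*Combined protocol and SAP*

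**What the plan says.** Section 10.2 bases the figure of about 3,200 subjects on the primary endpoint. It then turns to the follow-up endpoints because "it is appropriate to estimate whether the indicated sample can yield reliable information also in relation to such endpoints".

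Assuming that almost everyone is observed for at least one year, it claims 80% power at two-tailed 95% confidence for a Cohen's "effect of the baseline decision taken on the follow-up outcomes, of 0.055". From this it concludes that the survey can identify "deviations of at least one of the constituted sub-population from the anticipated recurrence rate" of at least ±0.0123, that is "3.77 or less, or 6.23 or more, events per 100 patients per year", against an expected 5 per 100. For bleeding or death, expected at 1 per 100, the deviation is ±0.0055, that is "0.45 or less, or 1.55 or more, events per 100 patients per year".

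The synopsis repeats both deviations, the first as "1.23 recurrence events from the expected rate of 5 events per 100 subjects per year", but at 97% confidence.

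On the analysis, section 10.4.3 says: "Deviations from the expected rate of events will be analyzed by chi square and/or time to event by survival analysis". The synopsis (Secondary endpoints) instead speaks of comparing proportions where appropriate.

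**The concern.** The power claim concerns one of three groups that divide the 3,200 subjects between them. A group holding a third of the sample carries a third of the information on its own event rate, so its detectable deviation must be wider than that of the whole cohort. The plan gives no expected group sizes, and none appears to enter its limits.

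The calculation is there to tell readers what the sample can show on endpoints that the plan itself calls clinically relevant. The DMSB also acts on analyses of these endpoints. Someone who trusts the 80% could read a non-significant result in one group as evidence against a deviation of the stated size, when the analysis had less than an even chance of detecting it.

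**Working it through.** **Inputs (section 10.2).** N = 3,200; w = 0.055; alpha 0.05 two-sided; expected rates p0 = 0.05 and 0.01; deviations d = 0.0123 and 0.0055; one year per subject. No group shares are given. The only distribution stated is the uniform null of the primary endpoint, so equal thirds (3,200/3 ≈ 1,067) is used as an assumption and varied below.

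**Step 1: reproduce the plan's figure.** The noncentrality is N·w² = 3,200 × 0.055² = 9.68. A 2-df chi-square then has power 80.2% at alpha 0.05 and 79.7% at 0.048. The stated 80% is confirmed. At the synopsis's alpha of 0.03 the same test has 73.9%.

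**Step 2: find how w became a rate.** Using d = w·√p0:
- recurrence: 0.055 × √0.05 = 0.0123
- bleeding/death: 0.055 × √0.01 = 0.0055

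These are exactly the plan's deviations. Reversing the step, N·d²/p0 = 3,200 × 0.0123²/0.05 = 9.68 and 3,200 × 0.0055²/0.01 = 9.68. All 3,200 subjects carry the deviation, and no group share appears. With a group of one third the noncentrality falls to 9.68/3 = 3.23, and the plan's own 2-df test then has 34% power.

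**Step 3: power by group size.** Exact equal-tailed one-sample binomial test against the expected rate, alpha 0.05, one year:

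| Group size (share) | 6.23 vs 5 | 3.77 vs 5 | 1.55 vs 1 | 0.45 vs 1 |
|---|---|---|---|---|
| 3,200 (all) | 84.5% | 91.4% | 80.7% | 94.0% |
| 1,600 (50%) | 58.4% | 62.0% | 51.1% | 70.3% |
| 1,067 (one third) | 39.2% | 46.3% | 39.2% | 47.6% |
| 640 (20%) | 27.2% | 30.1% | 20.0% | 21.7% |
| 320 (10%) | 14.8% | 14.6% | 12.8% | 0% |

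For example, at n = 1,067 the test of the recurrence rate rejects at 39 or fewer, or 69 or more, events. The 0% arises because even zero events among 320 is not significant: 0.99³²⁰ = 0.040, above 0.025.

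**Step 4: vary the choices at one third.**
- Normal approximation, one year: 41–46%.
- Chi-square comparing the three groups with each other, one group deviating, one year: w is only 0.024–0.029 and power is 21–29%.
- Two full years for everyone (2 × 1,067 = 2,134 observations), exact one-sample test: 68.4%, 75.7%, 59.9% and 82.8%, in the column order above.

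**Step 5: limits that do have 80% power.** Exact one-sample test, alpha 0.05, one year, per 100 per year, to two decimals:

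| Group size | Recurrence (lower / upper) | Bleeding or death (lower / upper) |
|---|---|---|
| 1,600 | 3.52 / 6.62 | 0.40 / 1.82 |
| 1,067 | 3.25 / 7.08 | 0.29 / 2.01 |
| 640 | 2.82 / 7.69 | 0.13 / 2.48 |
| 320 | 2.01 / 9.02 | none / 3.18 |

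**The case against.** **The shares are unknown.** The plan assumes no shares, and its primary alternative is that they are unequal. So 39–48% is one point on a curve. This stands, and the table is given for that reason. On a 1-df chi-square, though, a group would need about 80% of the sample to reach about 80% power in one year.

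**The exact binomial is not the planned test and is conservative in small groups.** Also true. A one-sample score test raises the power for 6.23 and 1.55 to about 33% and 29% at n = 640, and to about 20% and 23% at n = 320. At one third the choice hardly matters. The 2 df in the plan's calculation suggest a comparison between groups, but that reading gives lower power still (21–29%).

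**Follow-up lasts two years, and one year is only a floor.** One year is the basis that section 10.2 itself uses. Two full years for all is an upper bound, because follow-up stops at a thromboembolic event, a major bleed or a treatment change. Section 10.4.4 says "Any change in therapy, instead, implies interruption of the follow-up", although section 8.3.1 exempts dose changes. Even that bound gives 60–83% at one third; at one half it gives 81–94%.

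**The analyses are exploratory.** Section 10.1 says so, and the planned confidence intervals will show the precision achieved. This limits the consequence. It does not make the power statement correct.

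**Conclusion.** The power statement is wrong as written. The fault lies in converting w to event rates, which leaves out the sub-population's share. At equal thirds and one year, power for the stated deviations is 39–48% against the expected rate, and 21–29% if the groups are compared with each other, instead of 80%. On that basis a true deviation of the stated size would be missed more often than found. With two full years for everyone, about 80% is reached only by a group of roughly half the sample; at one third it is reached only for the lower bleeding/death limit.

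The exact percentages rest on the assumed shares, the chosen test and alpha 0.05. The omission of the share rests on none of these. The study size is not in question.

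Separately, the same limits cannot carry 80% power at both 95% and 97% confidence under the 2-df test: at alpha 0.03 it gives 73.9%.

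**What to change.** In section 10.2 and the synopsis:

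1. Name the test for the follow-up endpoints: each group against the expected rate, or the groups against each other.
2. State the assumed sub-population shares, with a range.
3. Either keep ±1.23 and ±0.55 and report the power they have at those shares, or replace them with limits by group size. The step 5 table serves if the one-sample exact test is chosen.
4. Say whether alpha is shared across the three group tests. At n = 1,067 with one group deviating, dividing alpha by three lowers the power for that group to 23–29%. Leaving it undivided gives about a 12% chance of at least one false signal when no group deviates.
5. Reconcile the synopsis (97% confidence, critical P of 0.03) with section 10 (95%, 0.048).

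The cost is a text change and a less favourable statement of sensitivity. No additional patients are needed.
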